5.2.1.2 Dose Modification

Adverse events (both non-serious and serious) associated with pembrolizumab exposure may represent an immunologic etiology. These adverse events may occur shortly after the first dose or several months after the last dose of treatment. Pembrolizumab must be withheld for drug-related toxicities and severe or life-threatening AEs as per Table 3 below. See Section 5.6.1 and Events of Clinical Interest Guidance Document for supportive care guidelines, including use of corticosteroids.

Table 3
Dose Modification Guidelines for Drug-Related Adverse Events

General instructions:				
Immune-related AEs	Toxicity grade or conditions (CTCAEv4.0)	Action taken to pembrolizumab	irAE management with corticosteroid and/or other therapies	Monitor and follow-up
Pneumonitis	Grade 2	Withhold	
 Administer corticosteroids (initial dose of 1-2 mg/kg prednisone or equivalent) followed by taper Add prophylactic antibiotics for opportunistic infections 	
 Monitor participants for signs and symptoms of pneumonitis Evaluate participants with suspected pneumonitis with radiographic imaging and initiate corticosteroid treatment
	Grade 3 or 4, or recurrent Grade 2	Permanently discontinue		
Diarrhea / Colitis	Grade 2 or 3	Withhold	
 Administer corticosteroids (initial dose of 1-2 mg/kg prednisone or equivalent) followed by taper 	
 Monitor participants for signs and symptoms of enterocolitis (ie, diarrhea, abdominal pain, blood or mucus in stool with or without fever) and of bowel perforation (ie, peritoneal signs and ileus).

	Grade 4 or recurrent Grade 3	Permanently discontinue		
 Participants with \geq Grade 2 diarrhea suspecting colitis should consider GI consultation and performing endoscopy to rule out colitis. Participants with diarrhea/colitis should be advised to drink liberal quantities of clear fluids. If sufficient oral fluid intake is not feasible, fluid and electrolytes should be substituted via IV infusion.
AST / ALT elevation or Increased bilirubin	Grade 2 ^a	Withhold	
 Administer corticosteroids (initial dose of 0.5- 1 mg/kg prednisone or equivalent) followed by taper 	
 Monitor with liver function tests (consider weekly or more frequently until liver enzyme value returned to baseline or is stable

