6.0 TRIAL FLOW CHART

6.1 Study Flow Chart

	Screening Period	Treatment Phase			End of treatment ⁶	Long-term Follow-up ⁷
		Window Cycles (1-6)	Response assessment ⁸	Continuation Cycles (7-18) ⁹		
Scheduling and Timing	-42 to -1d	+/- 3d		+/- 3d		
Informed consent	X					
Inclusion/Exclusion criteria	X					
Medical history	X					
Medication review (prior and concomitant)	X	X		X		
Trial treatment administration		X		X		
Post-study anticancer therapy status						X
Survival status						X
Vital signs	X	X		X	X	
Physical exam	X	X		X	X	
ECOG performance status	X	X		X	X	
Adverse event assessment ¹	X	X		X	X	
CBC and differential	X	X	X	X	X	
Comprehensive metabolic panel and LDH	X	X	X	X	X	
HepB SAg, Hep B Core Ab, HepC Antibody and HIV screen	X					
Urinalysis	X					
T3, FT4, and TSH	X	X		X	X	
PT/INR and aPTT	X					
Correlative studies blood draw	X		X		X	
Bone marrow studies ²	X					X
Pregnancy test ³	X					
Tumor assessment ⁵	X	X	X	X	X	
Archival Tissue collection ⁴	X					

¹Adverse events will be recorded from the time of a subject signing consent up until 30 days after the last dose of pembrolizumab, or 90 days after the last dose of pembrolizumab in the case of serious adverse events.

²If bone marrow involvement by iBCL was previously shown then repeat bone marrow exam at screening is not required as it is assumed positive. Otherwise, bone marrow studies include aspirate and unilateral biopsy and should be performed at screening unless a waiver is approved by the study Sponsor-Investigator or sub-Investigator. If all bone marrow studies are negative at screening, these do not need to be repeated. If bone marrow status is unknown or positive at screening, patients will need to have bone marrow study for confirmation of a CR.

³Pregnancy test is only required in women of childbearing potential.

⁴Archived tumor samples are requested for pathologic confirmation and biomarker analysis. If an archived specimen is not available or contains insufficient material, a fresh tumor biopsy (if clinically feasible) will be requested. Correlative studies may be performed on any available tissue.

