⁵Tumor assessment labs and/or imaging (see section 7.1.2.5) will be performed prior to cycle 4 (within 7 days of scheduled treatment dose) during the window phase. Tumor assessment will be performed prior to cycle 7 (within 7 days of scheduled treatment dose) to determine eligibility for continuation on study in continuation phase. Tumor assessment labs and/or imaging will be performed prior to cycles 11 and 15 (within 7 days of scheduled treatment dose) during the continuation phase, as applicable. Tumor assessment labs and/or imaging will be performed at end-of-treatment evaluation only for subjects who did not have tumor assessment labs and/or imaging performed within 60 days of end-of-treatment. Tumor assessment labs and/or imaging will also be performed as indicated per clinical standard of care (e.g. as appropriate for disease, to evaluate clinical suspicion of disease progression). Patients who have stable disease or asymptomatic radiologic disease progression prior to cycle 7 will remain in the window phase with restaging prior to cycle 10 to evaluate for pseudoprogression or delayed response. Patients who have restaging prior to cycle 10 are not required to have tumor assessments prior to cycle 11. Patients who have radiologic disease progression with doubling of tumor size prior to cycle 7 will be categorized as hyperprogression and will not proceed to the continuation phase.

⁶End-of-treatment evaluations should be done within 30 days (+/- 14 days) of the last dose of pembrolizumab or prior to the start of a new anti-cancer drug, whichever is first.

⁷Long-term follow-up should be done according to the patient's physician standard of care. This may be performed at patients' local physician's offices. Long-term follow-up will assess survival and disease progression; for clarification, subjects may be contacted by the study team until death, subject withdrawal of consent, lost to follow-up, or study termination, whichever occurs first.

⁸Response assessment will be performed prior to cycle 7 (within 7 days of scheduled treatment dose) only for those subjects that complete 6 cycles of treatment in the window phase.

⁹During treatment in the continuation phase, clinical assessment (physical exam including performance status, adverse event and medication review) will be performed on day 1 (+/- 3 days) of each odd-numbered cycle only, or as clinically indicated. Studies performed for response assessment⁹ do not need to be repeated prior to cycle 7.

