7.1.5.3 End-of-treatment Visit

Thirty days (+/- 14 d) after the last dose of pembrolizumab, irrespective of cause of cessation, an end-of-treatment visit should be performed. However, if a subject requires additional anti-cancer therapy, the off-study visit may occur earlier.

The off-study visit will include laboratory studies, medical history, physical exam, remission status, concomitant medications, adverse events, and documentation of any ECI and subsequent management, as in Section 6.0. All AEs that occur prior to the end-of-treatment visit should be recorded. Subjects with an AE of Grade > 1 will be followed until the resolution of the AE to Grade 0-1 or until the beginning of a new anti-neoplastic therapy, whichever occurs first. SAEs that occur within 90 days of the end of treatment or before initiation of a new anti-cancer treatment should also be followed and recorded.

After the end-of-study visit, additional follow-up will be conducted as per routine standard of care for up to 5 years unless other criteria for withdrawal are met (see Section 5.6). Long-term follow-up may be performed at patients' local physician's offices. Long-term follow-up will assess survival and disease progression; for clarification, subjects may be contacted by the study team until death, subject withdrawal of consent, lost to follow-up, or study termination, whichever occurs first.

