7.2 Assessing and Recording Adverse Events

An adverse event is defined as any untoward medical occurrence in a patient or clinical investigation subject administered a pharmaceutical product and which does not necessarily have to have a causal relationship with this treatment. An adverse event can therefore be any unfavorable and unintended sign (including an abnormal laboratory finding, for example), symptom, or disease temporally associated with the use of a medicinal product or protocol-specified procedure, whether or not considered related to the medicinal product or protocol-specified procedure. Any worsening (i.e., any clinically significant adverse change in frequency and/or intensity) of a preexisting condition that is temporally associated with the use of the Merck's product, is also an adverse event.

Merck product includes any pharmaceutical product, biological product, device, diagnostic agent or protocol-specified procedure, whether investigational (including placebo or active comparator medication) or marketed, manufactured by, licensed by, provided by or distributed by Merck for human use.

Adverse events may occur during the course of the use of Merck product in clinical trials or within the follow-up period specified by the protocol, or prescribed in clinical practice, from overdose (whether accidental or intentional), from abuse and from withdrawal.

Adverse events may also occur in screened subjects during any pre-allocation baseline period as a result of a protocol-specified intervention, including washout or discontinuation of usual therapy, diet, placebo treatment or a procedure.

Progression of the cancer under study is not considered an adverse event unless it is considered to be drug related by the investigator.

Adverse events grade 3 and higher, as well as AEs requiring clinical intervention/dose modification, ECIs and SAEs of any grade, will be recorded from the time the consent form is signed up until 90 days following the last dose of pembrolizumab and at each examination on the Adverse Event case report forms/worksheets. The reporting timeframe for adverse events meeting any serious criteria is described in section 7.2.3.1.

7.2.1 Definition of an Overdose for This Protocol and Reporting of Overdose to Merck

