7.2.3 Reporting of Adverse Events/Adverse Reactions

7.2.3.1 Serious Adverse Events

A serious adverse event is any adverse event occurring at any dose or during any use of Merck’s product that:

- Results in death;
- Is life threatening;
- Results in persistent or significant disability/incapacity;
- Results in or prolongs an existing inpatient hospitalization;
- Is a congenital anomaly/birth defect;
- Is a new cancer (that is not a condition of the study);
- Is associated with an overdose;
- Is an other important medical event

Refer to Table 6 for additional details regarding each of the above criteria.

Any serious adverse event, or follow up to a serious adverse event, including death due to any cause other than progression of the cancer under study that occurs to any subject from the time the consent is signed through 90 days following cessation of treatment, or the initiation of new anti-cancer therapy, whichever is earlier, whether or not related to Merck product, must be reported within 2 business days of investigator knowledge to Merck Global Safety.

Non-serious Events of Clinical Interest will be forwarded to Merck Global Safety and will be handled in the same manner as SAEs.

Additionally, any serious adverse event, considered by an investigator who is a qualified physician to be related to Merck product that is brought to the attention of the investigator at any time outside of the time period specified in the previous paragraph also must be reported immediately to Merck.

SAE reports and any other relevant safety information are to be forwarded to the Merck Global Safety [contact]

A copy of all 15 Day Reports and Annual Progress Reports is submitted as required by FDA, Pharmaceutical and Medical Devices agency (PMDA) or other local regulators. Investigators will cross reference this submission according to local regulations to the Merck Investigational Compound Number (IND, CSA, etc.) at the time of submission. Additionally, investigators will submit a copy of these reports to Merck & Co., Inc. (Attn: Worldwide Product Safety; [contact]) at the time of submission to FDA.

All subjects with serious adverse events must be followed up for outcome.

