7.2.3.2 Events of Clinical Interest

Selected non-serious and serious adverse events are also known as Events of Clinical Interest (ECI). See appendix 11.10, ECI Guidance Document, for management and reporting of ECI. ECI and must be recorded as such on the Adverse Event case report forms/worksheets and reported within 2 business days of investigator knowledge to Merck Global Safety. (Attn: Worldwide Product Safety; [contact]) Events of clinical interest for this trial include:

1. An overdose of Merck product, as defined in Section 7.2.1 - Definition of an Overdose for This Protocol and Reporting of Overdose to Merck, that is not associated with clinical symptoms or abnormal laboratory results.
2. An elevated AST or ALT lab value that is greater than or equal to 3X the upper limit of normal and an elevated total bilirubin lab value that is greater than or equal to 2X the upper limit of normal and, at the same time, an alkaline phosphatase lab value that is less than 2X the upper limit of normal, as determined by way of protocol-specified laboratory testing or unscheduled laboratory testing. *

***Note:** These criteria are based upon available regulatory guidance documents. The purpose of the criteria is to specify a threshold of abnormal hepatic tests that may require an additional evaluation for an underlying etiology. The trial site guidance for assessment and follow up of these criteria can be found in the Investigator Trial File Binder (or equivalent).

1. Additional adverse events:

A separate guidance document has been provided entitled “Event of Clinical Interest Guidance Document” (previously entitled, “Event of Clinical Interest and Immune-Related Adverse Event Guidance Document”). This document can be found in Appendix 4 and provides guidance regarding identification, evaluation and management of ECIs and irAEs.

ECIs (both non-serious and serious adverse events) identified in this guidance document from the date of first dose through 90 days following cessation of treatment, or 30 days after the initiation of a new anticancer therapy, whichever is earlier, need to be reported within 2 business days to Merck Global Safety. (Attn: Worldwide Product Safety; [contact]), regardless of attribution to study treatment, consistent with standard SAE reporting guidelines.

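### Key safety events must be recorded to day 90 after the last dose, but the last scheduled adverse-event assessment is at day 16 to 44, so capture of new late events is passive and unstandardised

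*Combined protocol and SAP*

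**What the plan says.** **Recording window.** Section 7.2 states that Grade 3 or higher adverse events, events needing clinical intervention or dose modification, and all SAEs and ECIs whatever their severity "will be recorded from the time the consent form is signed up until 90 days following the last dose of pembrolizumab". Section 7.2.5 repeats the same classes and the same 90 days. ECIs are reportable "from the date of first dose through 90 days following cessation of treatment, or 30 days after the initiation of a new anticancer therapy", if that is sooner (Section 7.2.3.2). SAEs are reportable "through 90 days following cessation of treatment, or the initiation of new anti-cancer therapy, whichever is earlier" (Section 7.2.3.1). Flow-chart footnote 1 ends general adverse-event recording at 30 days and allows "90 days after the last dose of pembrolizumab in the case of serious adverse events".

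**Scheduled assessments.** "Thirty days (+/- 14 d) after the last dose of pembrolizumab, irrespective of cause of cessation, an end-of-treatment visit should be performed" (Section 7.1.5.3). Footnote 6 brings that visit forward if a new anti-cancer drug is started. In the flow chart (Section 6.1), the adverse-event row is marked at screening, window cycles, continuation cycles and end of treatment, and is blank under long-term follow-up. The long-term column is marked only for post-study therapy, survival and bone marrow. Footnote 7 says "Long-term follow-up will assess survival and disease progression". It leaves the visits to the physician's standard of care, possibly at a local office, and permits but does not require contact by the study team.

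**Expected timing of events.** On adverse events with a possible immune cause, Section 5.2.1.2 says: "These adverse events may occur shortly after the first dose or several months after the last dose of treatment".

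**The concern.** The length of the recording window is not in question. The issue is how an event inside it reaches the trial. A 90-day obligation produces comparable data only if someone asks every subject about events up to day 90. Here the schedule of asking stops well before the schedule of recording, in a drug class for which the protocol itself expects some late onset.

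Safety and toxicity is the first secondary objective (Section 3.2), and Section 8.3.2.4 plans frequency tables by severity and relationship to drug. If late events are found only through unscheduled routes, the counts depend on where a subject is followed and how well the local office communicates with the site. A missed event can only lower a count, so any error runs towards under-reporting.

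**Working it through.** **Inputs.** End of the recording window: day 90 after the last dose (Sections 7.2 and 7.2.5). End-of-treatment visit: 30 +/- 14 days after the last dose (Section 7.1.5.3). Adverse-event entries after that visit: none (Section 6.1).

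**Step 1, the visit window.** Earliest 30 - 14 = day 16; latest 30 + 14 = day 44.

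**Step 2, days with no scheduled safety contact (no new therapy started).**
- Visit on day 44: 90 - 44 = 46 days; 46/90 = 51%.
- Visit on day 30: 90 - 30 = 60 days; 60/90 = 67%.
- Visit on day 16: 90 - 16 = 74 days; 74/90 = 82%.

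**Step 3, subjects who start new anticancer therapy on day T.** The visit moves to before T and may fall before day 16. The SAE reporting window closes at T, so the SAE gap is about zero if the visit comes just before T. The ECI window closes at the earlier of day 90 and T + 30, so that gap is then at most about 30 days. The 46 to 74 days do not apply to these subjects under the reporting rules. Sections 7.2 and 7.2.5, however, state no cut-off at new therapy, so on their wording recording still runs to day 90.

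**Step 4, other routes by which a new late event could be found.**
- Section 7.1.5.3 says SAEs within 90 days should be followed and recorded. This says what to do with an event, not how the site learns of it.
- Section 7.1.5.3 follows adverse events above Grade 1 until they settle to Grade 0-1 or new therapy begins, and the ECI guidance (3.13) follows subjects to resolution. Both concern events already known.
- Section 7.2 also calls for recording at each examination, and Section 7.1.2.1 mentions the follow-up period. Section 7.1.2.1 ties assessment to the flow chart, or more often if clinically indicated, and the chart has no entry after end of treatment.
- The ECI guidance overview allows ECIs to be found by spontaneous report or by review of subject data. No review is dated.
- Section 10.1 compares research data with the medical record, with no post-treatment timing. Some of those records may sit with local physicians.
- Section 5.3.1 records later concomitant medication for SAEs and ECIs, which presupposes that the event is known.
- Footnote 7 lets the study team contact subjects. This is optional, undated and written in the context of survival and progression.

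So several routes exist, but none is scheduled and none puts the question to every subject.

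**Step 5, the windows against each other.** Take a non-serious ECI on day 60. Footnote 1 and Section 5.6 stop non-serious events at 30 days, so it falls outside. Sections 7.2, 7.2.3.2 and 7.2.5 include it. For SAEs, Section 5.6 uses permissive wording for collection to day 90, whereas Sections 7.2 and 7.2.5 make it mandatory.

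**The case against.** The best defence is that the plan places real duties on the site after the end-of-treatment visit (Step 4), that serious events usually come to notice, and that the reporting windows shorten when new therapy starts. This is also a 33-patient single-arm pilot with response rate as its primary endpoint. Its safety analysis is a descriptive table of treatment-emergent events, with no planned ECI rate and no day-90 estimate.

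Much of this stands. It limits the point in two ways that a reader might otherwise miss.

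**A reader might infer that late events count only if patients volunteer them.** The documents do not support that. The recording duties, the follow-up of open events, data review, record checks and optional contact are all further routes.

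**A reader might infer that the toxicity suspension rule in Section 8.2 is biased by a calculable amount.** The documents do not support that either.
- They give no share of qualifying events that fall in the gap or go unnoticed, so any computed loss would only return the assumed share.
- The rule states no period for counting an event.
- It counts patients, so a late event in someone already counted changes nothing.
- Many late events would come after accrual. With 18 cycles of 21 days, the last dose is 17 x 21 = 357 days after the first, so the gap opens at 357 + 16 = 373 to 357 + 44 = 401 days. With 18 months (about 547 days) of accrual, it opens before accrual ends only for those enrolled in the first 547 - 401 = 146 to 547 - 373 = 174 days, roughly five to six months. Subjects who stop early reach it sooner.

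What the defence does not answer is that none of the remaining routes is dated or applied to every subject. A duty to record does not substitute for a scheduled question.

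**Conclusion.** The point holds as a mismatch between the recording obligation and the visit schedule. For subjects who start no new anticancer therapy, 46 to 74 of the 90 days carry no scheduled safety contact. Capture of new events in that stretch is passive and unstandardised, and the post-treatment safety tables may under-count them. The size of any under-count cannot be derived from the documents, and no effect on the suspension rule is claimed.

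This rests on three assumptions: the end-of-treatment visit takes place within its stated window; standard-of-care visits do not routinely collect adverse events for the trial; and events to day 90 enter the safety tables, since Section 8.3.2.4 does not say how far treatment-emergent extends. It is a cheap improvement and does not bear on the primary endpoint.

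**What to change.** 1. Add one study-team telephone contact at about day 90 after the last dose (for example, up to 7 days later) to the adverse-event row of the flow chart, to footnote 7 and to Section 7.1.5.3. It should ask about every class that Sections 7.2 and 7.2.5 require to that day: Grade 3 or higher adverse events, events needing intervention or dose modification, ECIs and SAEs.
2. For subjects who start new anticancer therapy, time the contact to the cut-offs in Sections 7.2.3.1 and 7.2.3.2, and say whether those cut-offs also limit recording under Sections 7.2 and 7.2.5.
3. Reconcile the 30-day and permissive wording in Section 5.6 and flow-chart footnote 1 with the 90-day requirement in Sections 7.2 and 7.2.5.

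The cost is staff time for at most 33 calls, plus the text edits. No visit, test or patient is added, and footnote 7 already permits the study team to contact subjects.
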